#### **Research Strategy**

#### **Background and Significance**

Multiple sclerosis (MS) is a chronic inflammatory disease of the central nervous system (CNS) affecting 2-3 million people worldwide and an estimated 1 million in the United States. Pathophysiologically, MS is characterized by axonal or neuronal loss, demyelination, and astrocytic gliosis. The neurodegenerative component of MS (axonal and neuronal loss) is thought to be the underlying mechanism associated with clinical disability. The mechanisms associated with axonal loss are primarily due to mitochondrial dysfunction occurring in both the acute and chronic phases of the disease, and decreased myelin trophic support, more commonly found in the chronic disease state. A plethora of disease-modifying pharmacological treatments have been developed primarily targeting neuroinflammation but not neurodegeneration. Therefore, the greatest unmet need is the identification of treatment approaches that incorporate neuroprotection and remyelination to delay, prevent, or reverse disease progression.

While a myriad of disease-modifying pharmacological treatment options have been discovered for the treatment of MS, rehabilitation research has neglected to identify innovative interventions that are disease-modifying or result in meaningful, long-term functional change. Current approaches to MS rehabilitation involve therapies that address deficits at the impairment and functional limitation level of the disability spectrum. Strength training, stretching, and functional mobility training aimed at improving walking ability and balance are foundational approaches commonly used in clinical practice environments. While all of these are considered supportive in nature, none are effective in modifying the long-term prognosis of MS. Numerous systematic reviews and meta-analyses have been conducted to examine the evidence of the effects of exercise training on physical fitness, fatigue, gait, balance, cognition, depressive symptomology, and self-reported quality of life. In general, targeted, task-specific interventions have been found effective in improving the consequences of MS: strength training improves strength, gait training improves gait, balance training improves balance, and so on. From a mechanistic perspective, improvements in these domains are likely induced by a training effect on the peripheral neuromuscular system. However, none of these training approaches target the CNS and studies investigating exercise efficacy in MS have not been designed with the end goal of altering CNS function. Thus, the potential for exercise to aide in neuroprotection, neuroplasticity, and to attenuate neural inflammation has not been tested empirically in persons with MS.

#### **Scientific Premise**

Several hypotheses have been proposed explaining the relationship between aerobic exercise (AE) and the global behavioral responses observed related to brain function. Aerobic exercise has been shown to increase cerebral blood flow, promote angiogenesis, and is associated with increased levels of dopamine, brain-derived neurotrophic factor (BDNF) and Insulin-like growth factor-1, all of which have been implicated in neuroplasticity and enhanced learning. Increased concentrations of endogenous neurotrophins have been implicated as the mechanism for improved cognition, learning, and memory in healthy older adults. Animal studies have shown enhanced motor training and recovery with high-intensity AE, resulting in lasting neuronal changes within the brain. In stroke rehabilitation, it has been posited that increased levels of neurotrophic factors and neurotransmitters are critical in facilitating the neural reorganization that likely underlies motor recovery. Therefore, there is substantial scientific rationale to hypothesize that AE, which results in increased levels of neurotrophic factors and neurotransmitters, could be used to “prime” the CNS to further enhance motor recovery post-stroke.

Klotho, a proposed anti-aging protein, has been identified to have a neuroprotective effect by inhibiting oxidative stress and promoting oligodendrocyte maturation, myelination, and (importantly) remyelination in mouse models. In mice, the upregulation of Klotho revealed reverses in age-related deterioration in the physiological functioning of numerous tissues. It is known that Klotho levels decline with age in healthy humans resulting in decreased resistance to oxidative stress. It has been shown that this decline in serum

Klotho levels can be combatted with aerobic exercise. In healthy patients, levels of serum Klotho were shown to increase, both acutely and long term, following high-intensity exercise. Levels of serum Klotho were also higher in highly trained athletes compared to healthy controls. Currently, it is unknown whether patients with MS can have increased serum Klotho levels in response to exercise, and whether this contributes to the positive effects of exercise seen in this population. Furthermore, it is unknown if patients with MS are capable of achieving an exercise intensity high enough to trigger increases in serum Klotho.

Advances in magnetic resonance imaging (MRI) techniques now allow for the assessment of structural and functional connectivity, through diffusion tensor imaging (DTI) and resting state functional MRI (rsfMRI). DTI measures can be used to assess tissue integrity, and are thought to reflect the degree of demyelination and axonal loss in pwMS. RsfMRI measures the strength of connection of functional pathways throughout the CNS, and thus changes may reflect neuroplasticity. The transcallosal and posterior cingulum bundle pathways represent motor and cognitive functions, respectively, and changes in structural and functional connectivity within these pathways have been proposed as a metric for longitudinal evaluation of functional decline in pwMS. In mouse models of stroke, voluntary exercise led to enhanced myelin density recovery (measured by DTI) and increased functional connectivity (measured by rsfMRI). However, it is unknown whether exercise promotes changes in structural or functional connectivity in pwMS, or whether these may correlate with positive effects of exercise seen in this population.

### **Innovation**

It is well documented that exercise participation elicits general benefits including improvements in physiological variables such as strength, aerobic capacity, walking; symptoms such as fatigue and pain; and quality of life. As such, exercise recommendations have been created with these primary endpoints in mind, potentially overlooking the ability of exercise to influence CNS function. Substantial evidence exists both in animal and human literature that aerobic exercise (AE) training may facilitate neuroplasticity. As it relates to MS, AE has the potential to enhance neuroplastic markers and attenuate neural inflammation, both critical targets in the restoration of function. However, previous studies investigating exercise efficacy have not prescribed exercise of sufficient intensity to elicit the neurophysiological effects necessary to alter CNS function. Forced exercise is an approach in which the voluntary efforts of the individual are augmented to allow them to exercise at a higher intensity than what they can achieve on their own. It is hypothesized that individuals with MS cannot sustain high rates of voluntary exercise (VE) necessary to trigger the endogenous release of neurotrophic factors which underlie neuroplasticity; therefore, forced exercise (FE) is necessary to overcome physical, behavioral and logistical barriers to improve motor function, QOL and participation in life activities.

### **Approach**

**The aim of this project is to conduct a pilot study to investigate the feasibility and initial efficacy of applying FE to individuals with MS to improve motor function, cognitive function, and QOL.**

**Experimental Overview:** A pilot study is proposed in which 20 individuals with MS presenting with an Expanded Disability Status Scale score between 2.0 and 6.5 will be eligible to participate. Participants will be screened using the American College of Sports Medicine Exercise Preparticipation Health Screening algorithm. The potential participant's physician will be notified of the study protocol and their patient's desire to participate. Eligible participants will undergo clinical and biomechanical assessments evaluating lower extremity function, processing speed, memory, and self-reported quality of life at baseline and post-intervention. Following baseline testing, participants will be randomized to undergo FE (n=10) or VE (n=10). Randomization will be stratified based on EDSS level (2.0-4.0 vs. 4.5-6.5) to facilitate comparable levels of disability in both groups. Participants in both groups will attend exercise sessions twice a week for 12 weeks. The FE intervention will consist of forced-rate aerobic exercise on a stationary semi-recumbent bicycle. Target cadence will be 80 revolutions per minute (RPM). Should the participant not tolerate the 80 RPM cadence, a self-selected cadence will be used initially, and increased by 5 RPM each session until the target cadence of 80 RPM is achieved. The VE intervention will be identical to FE, except participants will cycle at a self-selected cadence on a semi-recumbent stationary cycle ergometer without assistance from the motor. Aerobic intensity for both groups will be monitored continuously throughout the exercise using a heart rate chest strap. Target heart rate will be prescribed at 60-80% of the individual's age-predicted maximum. Following a 5-minute

warm-up, participants will complete a 35-minute main exercise set with the goal of maintaining their heart rate within the prescribed target zone. A 5-minute cool-down will occur immediately at the end of the 35-minute main exercise set. For the FE group, the cadence during warm up and cool down will be 15-20% less than the target cadence for the main exercise set (80 RPM) during the main exercise set. Water will be provided to the participant ad libitum, but all will be encouraged to drink 16-24 ounces during the exercise session. Cooling vests will be available to participants to avoid overheating as indicated. Rest breaks will be provided as requested, but all participants will be encouraged to progress to an entire 45-minute session without rest breaks.

**Recruitment and Sample:** Physicians and advance practice clinicians within the Mellen Center who would otherwise prescribe physical therapy to their patients will provide prospective participants with a study brochure. Should they express interest in learning more about the study, the study coordinator will call them to follow up. The study team may use MyChart as a way to contact eligible patients with an IRB approved flyer and/or brochure. Twenty-four patients will be recruited for this pilot feasibility study.

**Aim 1: To determine the feasibility of applying FE or VE training to individuals with MS.** Primary outcomes to determine feasibility will include measures of exercise compliance (percent of sessions attended, time spent exercising, time spent within target heart rate zone) and the absence of adverse events. The secondary outcomes will include change in levels fatigue and physical activity.

**Hypothesis 1:** Participants will comply with the FE or VE intervention (exercise frequency, time, and intensity) at  $\geq 90\%$  of the prescribed values and will present with no worsening fatigue or levels of sedentary activity following the FE or VE intervention.

**Aim 2: To determine the effects of a 12-week FE or VE intervention on motor function.** The primary outcome is change in biomechanical characteristics of gait. Secondary outcomes include changes in walking capacity, balance, manual dexterity test (MDT), and timed up and go (iTUG).

**Hypothesis 2:** Improvements in gait biomechanics and walking capacity will be observed following the 12-week FE intervention.

**Aim 3: To determine the effects of a 12-week FE or VE intervention on non-motor function.** The primary outcome measuring QOL is the change in the PROMIS-29 while the Multiple Sclerosis Performance Test (MSPT) and two measures of episodic memory (California Verbal Learning Test [CVLT], Brief Visuospatial Memory Test [BVMT]) will serve to measure cognitive function.

**Hypothesis 3:** Improvements in QOL and cognitive function will be measured following 12-weeks of FE and VE.

**Aim 4: To investigate the role of Klotho in promoting neuroprotection following FE or VE in pwMS.** For this exploratory aim, our outcomes will include change in serum Klotho expression acutely (pre- to post-exercise) and long-term (from baseline to post-intervention). We will also assess serum levels of neurofilament light (sNfL), a marker of axonal damage and biomarker of disease progression.

**Hypothesis 4:** The forced exercise group will achieve a higher level of exercise intensity, therefore promoting enhanced Klotho expression acutely (immediately post-exercise) and long-term (from baseline to post-intervention), which we hypothesize will correlate with lower levels of sNfL (i.e. enhanced neuroprotection) and improved motor and non-motor outcomes analyzed in aims 2-3.

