### **Data Variables**

**Exercise Training Variables:** Overall time, active exercise time, heart rate, cadence, and power are recorded in a secure, customized REDCap database. The primary training variables of interest for each exercise session are: AE intensity measured as percent heart rate reserve (%HRR) during main 35-minute exercise set, average cadence and work (power) produced by the patient and for the FE participants, by the motor.

**Measures of Feasibility (Aim 1):** Primary outcomes to determine feasibility will include measures of exercise compliance (percent of sessions attended, time spent exercising, time spent within target heart rate zone) and the absence of adverse events. Secondary outcomes will include change in levels fatigue and physical activity as measured by a body-worn activity monitor.

**Effects on Motor Function (Aim 2):** The primary outcome is change in biomechanical characteristics of gait, while the secondary outcomes include changes in walking capacity, manual dexterity test (MDT), and timed up and go (iTUG).

**Effects on Non-Motor Function (Aim 3):** The primary outcome measuring QOL is the change in the PROMIS-29, while the MSPT CVLT, and BVMT will serve as the primary outcomes measuring cognitive function.

**Role of Klotho (Aim 4):** The primary outcome is the acute and long-term change in serum Klotho levels from baseline to the post-exercise intervention, while the secondary outcome in long-term change in sNfL

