### **Outcomes:**

**Analysis of Feasibility (Aim 1):** Measures of compliance will determine feasibility of individuals with MS to complete the FE intervention. Self-reported fatigue will be measured using the Modified Fatigue Impact Scale. Activity levels will be measured using a Garmin Vivofit 4 body-worn activity monitor. The absence of adverse events will demonstrate safety of FE in MS.

**Biomechanical Gait Assessment (Aim 2):** The CAREN system is a complete biomechanical assessment system with 10 Vicon cameras, split-belt treadmill with two force plates, and D-flow software. Twenty-five retro-reflective markers will be placed at anatomic landmarks identified for LE assessment. Participants will walk at a self-selected pace for two 2-minute trials. The following biomechanical outcomes will be calculated: 1) spatio-temporal: velocity; cadence, step length, percentage of gait cycle spent in swing and stance phase, single and double limb support time and percentage; 2) Kinematic: hip and knee flexion and extension; ankle dorsi- and plantar-flexion; pelvic obliquity, rotation and tilt. To determine changes in overground walking, gait analysis will also be conducted using the Zeno Instrumented walkway. Participants will walk at a self-selected pace and fast pace for four lengths for each condition along the 15' Zeno Instrumented walkway. The following spatio-temporal outcomes will be calculated: velocity; cadence, step length, percentage of gait cycle spent in swing and stance phase, single and double limb support time and percentage. Lastly, the Timed up and Go will be administered.

**Non-Motor Function Data (Aim 3):** The PROMIS-29 will be administered to determine self-reported quality of life. The multiple sclerosis performance test (MSPT) and two measures of episodic memory, the California Verbal Learning Test and the Brief Visuospatial Memory Test, will be administered to examine change in cognitive function. All will be administered to determine feasibility with respect to administration approach, sensitivity to detect change over time, and time requirements for a future clinical trial.

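### Aim 1 judges forced-exercise feasibility on measures common to both arms; cadence and motor work, which define forced exercise, have no threshold and no link to the feasibility conclusion

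*Protocol*

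**What the plan says.** **Feasibility measures.** Aim 1 (protocol, Approach) names as primary outcomes "measures of exercise compliance (percent of sessions attended, time spent exercising, time spent within target heart rate zone) and the absence of adverse events". Data Variables repeats the list, opening with "Primary outcomes to determine feasibility will include measures of exercise compliance". Hypothesis 1 expects participants to "comply with the FE or VE intervention (exercise frequency, time, and intensity") at 90% or more of what was prescribed. Under Outcomes, the inference is stated directly: "Measures of compliance will determine feasibility of individuals with MS to complete the FE intervention".

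**What separates the arms.** The Experimental Overview makes VE the same as FE except that "participants will cycle at a self-selected cadence on a semi-recumbent stationary cycle ergometer without assistance from the motor". The FE target is 80 RPM. If that is not tolerated, "a self-selected cadence will be used initially, and increased by 5 RPM each session until the target cadence of 80 RPM is achieved".

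**What is recorded and analysed.** Data Variables lists, for each session, "AE intensity measured as percent heart rate reserve (%HRR) during main 35-minute exercise set, average cadence and work (power) produced by the patient", and for FE also the work done by the motor. The SAP summarises exercise parameters by group, models their change over sessions, and fits a mixed model for cadence with session, group and their interaction.

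**The concern.** Feasibility of FE is the pilot's lead question, and the Outcomes section looks ahead to a future clinical trial. A feasibility criterion for a new intervention should respond to whether the new element was delivered. Here each scored compliance measure applies in the same way to VE. The criterion can show that people with MS attend, pedal for the planned time and reach a heart-rate zone on a cycle. It is silent on whether they can be brought to, and kept at, the forced rate.

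Two things are at stake. A future trial could be planned on a positive Aim 1 result that did not test delivery of the forced rate. And if the FE and VE arms do not differ on the other outcomes, there would be no prespecified measure to help tell an ineffective intervention from one that was not delivered.

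**Working it through.** The documents state no figure for this point, so there is none to reproduce. The check compares the definitions and then does arithmetic on the protocol's own numbers.

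**Step 1. Does any compliance measure depend on cadence or the motor?**

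| Element | FE | VE | In the Aim 1 criterion? |
|---|---|---|---|
| Sessions, 2 × 12 = 24 | same | same | yes |
| Main set, 35 minutes | same | same | yes |
| Heart-rate zone | same | same | yes |
| Cadence | 80 RPM, or ramp to it | self-selected | no |
| Motor assistance | yes | no | no |

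The word *intensity* in Hypothesis 1 does not fill the gap. Data Variables measures intensity as heart-rate reserve and lists cadence and work as separate items. The Experimental Overview monitors it with a chest strap.

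**Step 2. What does 90% require now?** Attendance: 0.90 × 24 = 21.6, so 22 sessions. Main-set time: 0.90 × 35 = 31.5 minutes. Neither these nor time in zone contains cadence. An FE participant who stays below 80 RPM throughout has 0 of 24 sessions at target and can still score 100% on all three.

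**Step 3. Does the SAP cadence model supply the test?** The session-by-group interaction asks whether cadence trends differ between arms. An FE arm at 80 RPM from session 1 and an FE arm stalled at a lower cadence both have flat trends. The group term and the summaries would show the cadence level by arm, but no rule compares it with what was prescribed, and no sentence carries it into Aim 1.

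**Step 4. What would a delivery measure show?** For a starting cadence c, the cadence prescribed at session s is p(s) = min(80, c + 5(s − 1)). The documents give no starting cadences, so 40 to 75 RPM is an assumption. Each session is scored as achieved ÷ p(s), and the 24 scores are averaged.

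- *Follows the ramp exactly:* achieved = p(s), so the score is 100% from any start. From 40 RPM, (80 − 40)/5 = 8 sessions fall below 80, and the target is reached at session 9.
- *Stalls at c:* achieved = c in every session.

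| Stalled at (RPM, assumed) | Sum of session scores over 24 | Mean score | Meets 90%? |
|---|---|---|---|
| 40 | 580.2 + 16 × 50.0 = 1,380.2 | 57.5% | no |
| 60 | 358.0 + 20 × 75.0 = 1,858.0 | 77.4% | no |
| 70 | 193.3 + 22 × 87.5 = 2,118.3 | 88.3% | no |
| 75 | 100.0 + 23 × 93.75 = 2,256.3 | 94.0% | yes |

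The first term in each sum covers the sessions in which the prescribed cadence is still below 80. For 60 RPM, for example, it is 60/60 + 60/65 + 60/70 + 60/75 = 100.0 + 92.3 + 85.7 + 80.0 = 358.0.

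The present criterion can give 100% in all four stalled cases. The delivery measure separates the first three from a participant who follows the ramp. The 75 RPM case passes although 80 RPM is never reached, so the number who never reach target has to be reported separately.

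**The case against.** **Cadence is not ignored.** It is a listed training variable, summarised by arm and modelled over sessions. Failure of the arms to separate would be visible to anyone reading the output. This stands, and it limits the point: what is missing is a threshold and a link to the feasibility conclusion, not the data or all analysis of them.

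**The ramp is part of the procedure.** The protocol requires the increase at each session, and sessions are supervised. A stall is a departure from what is written, and nothing in the documents suggests how common it would be. This also stands. But the protocol foresees that some participants will not tolerate 80 RPM at first and does not say how to classify one who cannot follow the ramp. Detecting such cases is a purpose of a feasibility study.

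**The list of outcomes is not closed,** since the protocol says only what it will include. True, but no cadence threshold appears in either document.

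**Two stronger readings are tempting and are not supported.**

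- A reader might infer that FE could be declared feasible in people who never received it. FE differs from VE in motor assistance as well as cadence, and nothing says the motor is withdrawn while the fallback cadence is in use. A participant at a self-selected starting cadence is not thereby shown to have received VE.
- A reader might count sessions at exactly 80 RPM and conclude that ramping participants fall short. From assumed starts of 40, 50, 60 and 65 RPM, a perfect ramp gives 16, 18, 20 and 21 of 24 sessions at target (66.7%, 75.0%, 83.3% and 87.5%). These participants are following the protocol. Hypothesis 1 is set against prescribed values, and against the prescription for each session they score 100%.

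**Conclusion.** The concern holds in a limited form. The Aim 1 criterion contains no element that distinguishes FE from VE, yet the protocol uses it to conclude that FE can be completed. Cadence and motor work are collected, and cadence is analysed, but neither bears on that conclusion. A positive Aim 1 result would therefore not show that forced-rate cycling was deliverable.

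The size is a range of possibility, not an expected rate: an FE participant could have 0 of 24 sessions at 80 RPM and 100% on all three compliance measures. The illustrative scores of 57.5% to 94.0% for stalled participants rest on assumed cadences of 40 to 75 RPM, full attendance and no progress along the ramp. The main finding needs none of these assumptions; it follows from the definitions. The change is worth making because it concerns the lead question and costs little.

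**What to change.** For the FE arm, add a delivery component to Aim 1 and Hypothesis 1, and carry it into the SAP:

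- **Definition.** Achieved main-set cadence as a percentage of the cadence the protocol itself prescribes for that session: the ramp value while the ramp runs, then 80 RPM.
- **Denominator.** Active exercise time, so that permitted rest breaks, already reflected in time spent exercising, are not counted twice.
- **Criterion.** The existing 90%. State in advance whether it applies to each participant or to the arm mean, and how missed sessions enter the ramp count.
- **Reported beside it.** The motor's contribution to work, the number of sessions needed to reach the protocol's target, and the number of participants who never reach it.

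No change to the cadence rule or to the handling of participants is proposed.

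**Cost.** Protocol and SAP wording and a small amount of extra analysis. Data Variables already lists "average cadence and work (power) produced by the patient and for the FE participants, by the motor", so no new data are needed. The downside is that the FE feasibility figure may look less favourable.

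### Aim 1 counts zero adverse events, of any cause and in either arm, as a primary feasibility outcome and as the test of FE safety; one unrelated minor event means it is not met

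*Protocol*

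**What the plan says.** The protocol states the criterion three times.

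- **Approach, Aim 1.** The primary feasibility outcomes are three compliance measures and a safety item. The list ends with "time spent within target heart rate zone) and the absence of adverse events". The aim covers FE or VE.
- **Data Variables, Measures of Feasibility.** The list is repeated, again unqualified: "and the absence of adverse events. Secondary outcomes will include change in levels fatigue and physical activity".
- **Outcomes, Analysis of Feasibility.** Compliance is said to determine feasibility. A separate sentence reads: "The absence of adverse events will demonstrate safety of FE in MS".

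No section says which events count by cause, seriousness, severity or time window, and none gives a tolerable number. Pilot Study Methodology says when a session is stopped, but does not define an adverse event. The SAP does not mention adverse events.

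The one numerical feasibility threshold is in Hypothesis 1: "Participants will comply with the FE or VE intervention (exercise frequency, time, and intensity) at" 90% or more of the prescribed values, together with no worsening of fatigue or sedentary activity. Adverse events are not part of it.

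On numbers, the Experimental Overview says "participants will be randomized to undergo FE (n=10) or VE (n=10"), while Recruitment and Sample says "Twenty-four patients will be recruited for this pilot feasibility study". Exposure is given as "Participants in both groups will attend exercise sessions twice a week for 12 weeks".

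**The concern.** An outcome worded as the absence of something can be met only by a count of zero. Participants are aged 18 to 75 with EDSS 2.0 to 6.5 and are followed for 12 weeks. A cold, a fall at home or a fluctuation in MS symptoms could occur in any of them whether or not they cycle. As worded, each would count the same as an injury on the cycle, and an event in the VE arm would count the same as one in FE.

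The outcome then says little about FE. A missed outcome may reflect FE, cycling in general, or neither. The protocol also does not say what to conclude once one event has occurred. That reading would be chosen after the data are seen, by staff who know the arm. These results are meant to inform a future trial, so a safety outcome that can report only zero or not zero loses most of the useful information.

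**Working it through.** The documents give no event rate and no adverse-event threshold, so there is no figure to reproduce. The check asks how often the literal criterion would be met if exercise added no risk.

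**Inputs.** n = 10 (one arm) and n = 20 (both arms), from the Experimental Overview; n = 24, from Recruitment and Sample. The per-participant probability p of at least one event of any cause over 12 weeks is an assumption, taken as 5%, 10% and 20%. Participants are assumed independent.

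**Formula.** P(no participant has an event) = (1 − p)^n.

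| n | p = 5% | p = 10% | p = 20% |
|---|---|---|---|
| 10 (FE arm) | 0.95^10 = 60% | 0.90^10 = 35% | 0.80^10 = 11% |
| 20 (both arms) | 0.95^20 = 36% | 0.90^20 = 12% | 0.80^20 = 1.2% |
| 24 (recruited) | 0.95^24 = 29% | 0.90^24 = 8% | 0.80^24 = 0.5% |

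**Risk needed for a likely pass.** Setting (1 − p)^n = 0.80 gives p = 1 − 0.80^(1/n): 2.2% for n = 10, 1.1% for n = 20 and 0.9% for n = 24. An 80% chance of meeting the outcome therefore needs an all-cause 12-week risk of about 1% to 2% or less.

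**Discrimination, as an illustration.** Suppose the background risk is 10% and a harmful FE programme raises it to 20%. In the FE arm, the chance of not meeting the outcome is 1 − 0.349 = 65% if FE is harmless and 1 − 0.107 = 89% if it is harmful. The ratio is 0.893/0.651 = 1.4, so a missed outcome moves the evidence little. Over both arms, with VE at 10%, the chances are 1 − 0.122 = 88% and 1 − 0.349 × 0.107 = 96%, a ratio of 1.1.

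**What a zero count would show.** The exact one-sided 95% upper limit after zero events is 1 − 0.05^(1/n): 25.9% for n = 10, 13.9% for n = 20 and 11.7% for n = 24. Even when met, the criterion leaves a wide range of event risks open for FE.

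**Effect of restricting the events.** If only session-related or serious events counted, with an assumed risk of 1% to 2%, the chance of none in the FE arm would be 0.99^10 = 90% to 0.98^10 = 82%. A nonzero count would then be unusual under a safe programme, and so would carry information.

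**The case against.** The strongest reply is that the documents attach no decision to this item. There is no go/no-go rule. Hypothesis 1 leaves adverse events out, and the Outcomes section says that compliance determines feasibility. The safety sentence runs one way: no events would show safety, but nothing says that one event shows FE to be unsafe. All of this stands. A reader might infer that a single event makes Aim 1 fail or FE not feasible; the documents do not support that.

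A reader might also infer that the criterion would almost always be missed. The figures do not support this across the range: at a 5% risk it is met 60% of the time in FE and 36% of the time in 20 participants. Nor do the documents support a claim that staff would under-record minor events. That is conjecture.

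A further reply is that reading the criterion as any cause and any severity is drawn from silence, because adverse events are never defined or windowed. This is fair as a statement of what is missing. But the unqualified wording has that plain meaning, and nothing elsewhere narrows it. If only exercise-related events were intended, the text needs to say so before data are seen.

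Finally, the investigators could simply report counts by arm. They could, but the stated primary outcome is zero events, not a count.

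**Conclusion.** The point holds in a limited form. Read literally, one unrelated minor event in either arm means that this listed primary outcome is not met and leaves the FE safety statement without its stated basis. The outcome therefore distinguishes a safe from an unsafe FE programme poorly. It does not by any written rule decide Aim 1, because the three compliance measures are unaffected.

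The conclusion that one event is enough rests on the text alone. The size rests on assumed risks and on independence between participants. With 20 or 24 participants, missing the outcome is more likely than meeting it at every assumed risk from 5% to 20%. In the FE arm alone this is so at 10% and 20%, but not at 5%. The change is worth making because it concerns a stated primary outcome and costs little.

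**What to change.** In Approach (Aim 1), Data Variables (Measures of Feasibility) and Outcomes (Analysis of Feasibility), replace the all-or-none wording with the number and percentage of participants, by arm and with exact confidence intervals, who have:

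- (a) at least one adverse event judged related to an exercise or testing session; and
- (b) at least one serious adverse event of any cause, with its judged relatedness.

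Show all-cause counts by arm alongside, and state the period over which events are collected. In Outcomes, base the statement about FE safety on the FE-arm figures and their intervals, not on whether any event occurred. Add a matching sentence to the SAP, which has none on adverse events.

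The cost is wording and a relatedness field in data capture. The protocol describes its REDCap database only for exercise training variables, so an adverse-event form may also be needed. There is a small downside: relatedness is judged by staff who know the arm. The all-cause counts partly offset this.
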